#### Determination of Patients for Analysis:

All enrolled patients that received a BSC penile prosthesis with data available will be included.

### 8.3.3 EFFECTIVENESS OBJECTIVE 3 – EHS QUESTIONNAIRES

To assess erection hardness based on patients' most recent sexual encounters.

#### Endpoint:

The endpoint is the change in the single-item EHS scores from baseline to 1-year post-operative follow-up.

#### Statistical Analysis:

The EHS scores will be computed for each patient at baseline and 1-year follow up, and the change from baseline to 1-year follow up will be calculated. Descriptive summary statistics including mean, median, SD, and range will be generated by each device type and overall for all BSC penile prostheses recipients. For within patient change at 1-year follow up compared to baseline, signed rank sum test or paired t-test may be used when applicable.

Additional analyses may also be used to summarize the values at the other follow-up time points with data available along with changes from baseline for each device type and overall for all BSC penile prostheses recipients. Mixed effects model may be used to estimate the change from baseline across follow up visits when appropriate.

In addition, the number and percentage of patients who meet the following criteria will be calculated at baseline and each follow up visit for each device type and overall:

- Patients with an EHS score ≥ 3 (penis hard enough for penetration but not completely hard)
- Patients with an EHS score = 4 (penis completely hard and fully rigid)

#### Determination of Patients for Analysis:

All enrolled patients that received a BSC penile prosthesis with data available will be included.

### 8.3.4 EFFECTIVENESS OBJECTIVE 4 – SF-12 HRQOL QUESTIONNAIRES

To measure function health and well-being from the patient's point of view.

#### Endpoint:

The endpoint is the change in each of the following SF-12 scales from baseline to 1year post-operative follow-up.

Two component summary scales:

- PCS (physical component summary)
- MCS (mental component summary)

Eight individual domain scales:

- Physical functioning
- Role physical
- Emotional well-being
- Role emotional
- Social functioning
- Energy
- Pain
- General health

#### Statistical Analysis:

The PCS, MCS and individual domain scores will be computed for each patient at baseline and 1-year follow up, and the change from baseline to 1-year follow up will be calculated. Descriptive summary statistics including mean, median, SD, and range will be generated for each device type and overall for all BSC penile prostheses recipients. For within patient change at 1-year follow up compared to baseline, signed rank sum test or paired t-test may be used when applicable.

Additional analyses may also be used to summarize the values at the other follow-up time points with data available along with changes from baseline for each device type and overall for all BSC penile prostheses recipients. Mixed effects model may be used to estimate the change from baseline across follow up visits when appropriate.

#### Determination of Patients for Analysis:

All enrolled patients that received a BSC penile prosthesis with data available will be included.

### 8.3.5 EFFECTIVENESS OBJECTIVE 5 – AUA-SI/IPSS QUESTIONNAIRES

To quantify urinary irritative/obstructive symptom frequency and severity.

### Endpoint:

The endpoint is the change in the AUA-SI total scores from baseline to 1-year post-operative follow-up.

#### Statistical Analysis:

The AUA-SI total scores will be computed for each patient at baseline and 1-year follow up, and the change from baseline to 1-year follow up will be calculated. Descriptive summary statistics including mean, median, SD, and range will be generated for each device type and overall for all BSC penile prostheses recipients. For within patient change at 1-year follow up compared to baseline, signed rank sum test or paired t-test may be used when applicable.

Additional analyses may also be used to summarize the values at the other follow up time points with data available along with changes from baseline for each device type and overall for all BSC penile prostheses recipients. Mixed effects model may be used to estimate the change from baseline across follow up visits when appropriate.

In addition, the number and percentage of patients who meet the following criteria will be calculated at baseline and each follow up visit:

- Mild (0 to 7)
- Moderate (8 to 19)
- Severe (20 to 35)

### Determination of Patients for Analysis:

All enrolled patients that received a BSC penile prosthesis with data available will be included.

### 8.3.6 EFFECTIVENSS OBJECTIVE 6 – UCLA-PCI QUESTIONNAIRES

To assess disease-specific, organ targeted health related quality of life in six scales or domains that are of special concern to men treated for prostate cancer.

#### Endpoint:

The endpoint is the change in each of the following UCLA-PCI domains from baseline to 1-year post-operative follow up.

- Sexual Function
- Sexual Bother
- Urinary Function
- Urinary Bother
- Bowel Function
- Bowel Bother

#### Statistical Analysis:

The individual domain scores will be computed for each patient at baseline and 1-year follow up, and the change from baseline to 1-year follow up will be calculated. Descriptive summary statistics including mean, median, SD, and range will be generated for each device type and overall for all BSC penile prostheses recipients. For within patient change at 1-year follow up compared to baseline, signed rank sum test or paired t-test may be used when applicable.

Additional analyses may also be used to summarize the values at the other follow-up time points with data available along with changes from baseline for each device type and overall for all BSC penile prostheses recipients. Mixed effects model may be used to estimate the change from baseline across follow up visits when appropriate.

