- Relevant concomitant medical conditions and concomitant medications that might impact ED (premature or rapid ejaculation/PE, climacturia, cardiovascular disease, diabetes, Peyronie's disease, stress urinary incontinence/SUI, steroid use, anticoagulant use, anti-depressant use, venous leak, and Other, please specify) – with the following sub-

assessments if SUI checked:

- Etiology of incontinence (radical prostatectomy, pelvic irradiation, and other – please specify)
- Previous treatment(s) for incontinence (behavior modification, pelvic floor muscle training, transobturator male sling - specify model and implant date, artificial urinary sphincter/AUS – specify implant model date, other - specify)
- Number of pads used daily
- Pad weight (24-hour test)
- Urodynamics: Post-void residual (PVR) volume (ml), maximum flow rate (ml/sec), any detrusor overactivity (DO) or detruser sphincter dyssynergia (DSD)
- Cystoscopy findings (bladder neck contracture, other – specify)
- Pre-op flaccid penile length (measured from suprapubic fat pad to tip)
- Pre-op stretched penile length (measure from suprapubic fat pad to tip)
- Pre-op flaccid girth (circumference measured 1cm proximal to the proximal end of the corona)
- Duration of ED (years or months)
- Previous ED Treatments [ PDE-5 inhibitors (PDE-5s), vacuum erection device (VED), intracavernosal injection (ICI), Combination therapies, previous/failed penile implants), other, specify]
- Patient query any office visits in past year for treatment of depression Y/N
  - If Yes: approximately how many visits
  - If Yes: taking any depression medication
- Was VED and/or penile traction therapy prescribed pre-operatively? (Y/N)
  - If Yes: specify Duration (weeks) and Frequency (times/day)
- Baseline effectiveness/quality of life assessments

Implantation surgery data will include:

- Date of procedure
- Original (virgin), revision, salvage or replacement implant
  - If revision or salvage, washout (Y/N)

- Surgical approach (Penoscrotal (PS), Infrapubic (IP), Subcoronal (SC) or "Other, please specify")
- Implant model type:
  - Spectra™ Concealable Penile Prosthesis
    - Cylinder diameter (9.5, 12, 14 mm)
    - Cylinder length (12, 16, 20 cm)
    - Total number of RTEs per cylinder (0, 1, 2)
    - Total length of RTEs per cylinder (specify: 0.5 to 7.5 cm)
  - AMS Ambicor® Penile Prosthesis (2-piece inflatable)
    - Cylinder diameter (12.5, 14, 15.5 mm)
    - Cylinder length (14, 16, 18, 20, 22 cm)

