### 2.2 Registry Design Rationale

The selection of specific effectiveness data measurements in this Registry study was based on outcomes reported in published literature for a range of current ED treatment options, to allow for generalized comparisons between modern, prospective penile prosthesis outcomes and historical data for a variety of ED treatments.

Current recommendations for ED diagnosis, management and research from international evidence-based consensus panels were also consulted to determine which patient-reported outcomes (PROs) are measured as part of the standard of care for clinical evaluation and treatment of ED.

In both clinical practice and research, it has been recommended that ED severity be categorized using the International Index for Erectile Function EF domain (IIEF-EF). The IIEF-5 (also identified as the Sexual Health Inventory for Men or SHIM) is a validated and well established erectile function measure comprised of 5 of the 15 IIEF items, including 4 of the 6 IIEF-EF questions and one question from the intercourse satisfaction domain.  A single-item, validated erection hardness scale/score (EHS) is also commonly recommended and used.  These tools have been successfully employed to measure baseline and post-treatment erectile function and penile rigidity in many clinical trials of ED pharmacotherapy and devices as well as in clinical practice.

For patients with ED due to treatment of prostate cancer, the UCLA Prostate Cancer Index (UCLA-PCI) is a validated 20-item tool for measurement of health-related quality of life specific to sexual, urinary, and bowel function and bother; and has been employed in numerous published studies to demonstrate serial improvements or declines in the six domains commonly affected by prostate cancer treatment.  Each UCLA-PCI domain scale is scored on a scale of 0–100 points with higher values representing better outcomes. A difference of 5–10 points has been considered a clinically important change in a given domain. 

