Incontinence or urinary leakage and obstruction often accompanies ED after prostate cancer treatment, at least transiently, and is measured in clinical practice and research using pad counts and weights and validated PROs.  The American Urological Association Symptom Index (AUA-SI) is comprised of 7 of the 8 items of the International Prostate Symptom Score (IPSS), and has been widely used to report baseline and post-treatment clinical urinary symptom outcomes. 

General health-related quality of life (HRQOL) has been evaluated in many different disease state settings with serial assessments using the Short Form Health Survey (SF-12), which is a 12-item adaptation of the RAND 36-Item Health Survey (SF-36) that takes only two to three minutes to complete. The SF-12 (v2) is a practical, reliable, and valid measure of physical and mental health widely used in large population applications. The SF-12v2 is available in multiple modes of administration and in both standard four week and acute one week recall periods. The SF-12 quantifies HRQOL into two composite scores: the Physical Component Summary (PCS) and Mental

Component Summary (MCS) scales. This survey also quantifies HRQOL into the same eight multi-item subscale domains used in the SF-36 with one or two questions in each domain: physical functioning, emotional well-being, general health, pain, energy, social functioning, and role limitations (problems with work or other daily activities) as a result of physical or emotional health. Because this survey uses norm-based scoring, comparisons can be made between published outcomes from the broader SF-36 survey.

Additional measurements were identified for required and optional data collection in the Registry database based on interviews with physician Principal Investigators and their standard of care for management of patients with ED before and after implantation of a penile prosthesis. The two, simple, individual questions about device use and satisfaction with the device were selected based on this feedback and the published studies using similar single-item assessments, since there is no validated tool available at present to measure the outcomes associated with penile implants as a treatment for ED.

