### 7.3 PATIENT QUESTIONNAIRES

Patient questionnaires to measure effectiveness will be optional at baseline and at all follow-ups. The following validated, patient-reported outcome questionnaires are *strongly recommended* for all patients at baseline and follow-up:

- IIEF-5/SHIM erectile function questionnaire
- EHS erection hardness questionnaire
- SF-12 health-related quality of life (HRQOL) questionnaire

The following validated, patient-reported outcome questionnaires are recommended for all patients with post-prostatectomy ED or incontinence:

- AUA-SI/IPSS urinary symptom questionnaires
- UCLA-PCI urinary, sexual and bowel function and bother questionnaire

The questions for each individual questionnaire are provided in the Appendix.

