#### 8.3 EFFECTIVENESS OBJECTIVES

Effectiveness of the BSC penile prostheses will be assessed in all patients with data available at the required 1-year ( $\pm$  4 months) post-operative follow-up, and any of the following additional follow-up time points with data available:

- 3 months (± 1 month)
- 6 months (± 1 month)
- 18 months (± 1 month)
- 2 years (± 4 months)
- 3 years (± 6 months)
- 4 years (± 6 months)
- 5 years(± 6 months)

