#### Determination of Patients for Analysis:

All enrolled patients that received a BSC penile prosthesis with data available will be included.

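### Uncontrolled 1-year change in urinary, bowel and pad measures is listed as prosthesis effectiveness, without separating men given a concomitant sphincter or sling or allowing for change after prostate cancer treatment

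*Combined protocol and SAP*

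**What the plan says.** Section 8.3 opens: "Effectiveness of the BSC penile prostheses will be assessed in all patients with data available at the required 1-year" follow-up, plus other visits where data exist. Under that heading come the changes from baseline to 1 year in AUA-SI total score (8.3.5), in all six UCLA-PCI domains, including urinary and bowel (8.3.6), and in daily pads and 24-hour pad weight (8.3.7).

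The statistical paragraph is nearly the same in all three: descriptive summaries by prosthesis type and overall, then "For within patient change at 1-year follow up compared to baseline, signed rank sum test or paired t-test may be used when applicable". Sections 8.3.5 and 8.3.6 also allow a mixed model across visits; 8.3.7 does not mention one. The analysis set is the same throughout: "All enrolled patients that received a BSC penile prosthesis with data available will be included".

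Three other parts of the plan bear on this:

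- **Concomitant devices.** The synopsis (Concomitant Surgical Procedures) and section 4 allow an AMS 800 sphincter or AdVance sling to be implanted together with the prosthesis, and make these the exception for which outcome data are collected. The operation form records them under concurrent procedures, which section 7 lists as required data and section 8.5 summarises.
- **Background.** Section 2.2 says: "Incontinence or urinary leakage and obstruction often accompanies ED after prostate cancer treatment, at least transiently". It also says that UCLA-PCI has been used in published work to show "serial improvements or declines in the six domains commonly affected by prostate cancer treatment".
- **Who completes the forms.** Under section 7.3, AUA-SI and UCLA-PCI are "recommended for all patients with post-prostatectomy ED or incontinence". Pads are analysed only in men who were incontinent before surgery.

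**The concern.** For IIEF-5, EHS and the UCLA-PCI sexual domains, a before-after comparison has a direct reading, because the prosthesis supplies the erection. The plan gives no route by which a penile prosthesis would change bowel function, urinary symptoms or pad use. It does name two other sources of change. One is a second device put in at the same operation to treat incontinence. The other is the course of symptoms after prostate cancer treatment. The forms are directed to men in whom one or both are likely.

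With no comparator and no separation of these men, a mean improvement would appear in a prosthesis-effectiveness table whatever caused it. A decline from another cause would count against the prosthesis in the same way. Sections 8 and 18 plan publication of these results, so the label would carry through to the papers.

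**Working it through.** **1. What the mean change contains.** Let D be the mean prosthesis effect on a urinary, bowel or pad measure. Let a share s of men receive a sphincter or sling with mean effect c, and a share f be still changing after prostate cancer treatment by a mean of r. Then

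mean 1-year change = D + s·c + f·r + any other cause.

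The paired test asks whether the whole sum is zero. The data as analysed cannot isolate D. For the bowel domains only the f·r term is a natural candidate. For pads, pad weight and the UCLA-PCI urinary domains both terms apply.

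**2. Whether the planned breakdowns separate the terms.**

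| Source of change | Collected? | Used in 8.3.5 to 8.3.7? |
|---|---|---|
| Concomitant sphincter or sling | Yes, a required field (section 7), summarised in 8.5 | No; not named in 8.4.1 |
| Time since prostate cancer treatment | Not among the listed baseline data | No |
| Duration of ED | Listed in the synopsis, summarised in 8.4.3; not on the required list in section 7 | No |
| Etiology, including radical prostatectomy | Yes, required | Optional subgroup in 8.4.1; does not separate early from late |

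Reporting by prosthesis type does not help, since a sphincter or sling may accompany any type. The subgroup list in 8.4.1 is open-ended, so such splits are permitted, but none is specified.

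**3. Size, as an illustration.** The plan gives no alpha, SD, power or paired sample size for these endpoints, so there is no figure of its own to reproduce. Its only related arithmetic is 500 + 15 + 20 = 535 implants per enrollment year, which agrees with the stated expectation of more than 500. The number with paired urinary or bowel forms is not given.

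Inputs: D = 0. A share f of men changes by m points for another reason and the rest do not change. The values m = 5 and 10 are the clinically important UCLA-PCI difference in section 2.2, borrowed here as a scale and not as a recovery rate. Assumed: two-sided alpha 5%, SD of change 25, n = 50, 100 or 200.

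Mean change = f·m. SD = √(25² + f(1−f)m²). Noncentrality = f·m / (SD/√n), referred to the noncentral t distribution.

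Example with f = 0.25, m = 10, n = 200: mean change 2.5; SD = √(625 + 18.75) = 25.37; SE = 25.37/14.14 = 1.79; noncentrality 2.5/1.79 = 1.39; probability of p<0.05 = 28.4%.

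| Share f | m | Mean change | n=50 | n=100 | n=200 |
|---|---|---|---|---|---|
| 10% | 5 | 0.5 | 5.2% | 5.4% | 5.9% |
| 10% | 10 | 1.0 | 5.9% | 6.8% | 8.6% |
| 25% | 5 | 1.25 | 6.4% | 7.8% | 10.8% |
| 25% | 10 | 2.5 | 10.5% | 16.4% | 28.4% |
| 50% | 5 | 2.5 | 10.6% | 16.7% | 28.8% |
| 50% | 10 | 5.0 | 27.5% | 49.3% | 78.8% |

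With SD 20 and n = 200, simulation gives 6% to 11% for a 10% share, 18% to 54% for a 30% share and 42% to 93% for a 50% share (5 to 10 points in each case). With no such change the rate is 5%.

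These are not type I error rates. The mean change in these scenarios is not zero, so the test is right to reject. They are the chances that a change with another cause is declared significant under an effectiveness heading. The calculation is on the UCLA-PCI scale only; the documents give no basis for one on AUA-SI or pads.

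**The case against.** The strongest reply is that this is a descriptive, non-interventional registry. The tests are optional, and no hypothesis, alpha or success criterion is attached to these endpoints. Objectives 5 and 6 are worded as measuring symptoms and quality of life, and no sentence attributes urinary or bowel change to the prosthesis. All of that is true. What remains is that the change is calculated and summarised under prosthesis effectiveness whether or not a test is run, and the optional p-value invites a causal reading.

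A reader might go further and infer that the plan itself calls these problems often transient, so that recovery from cancer treatment is being credited to the device. The documents do not support that. In section 2.2, often describes how frequently urinary problems accompany ED, and the reference to transience sets a minimum duration. Bowel symptoms are not mentioned there, and the UCLA-PCI statement covers declines as well as improvements. Section 2.3 also describes the devices as intended for chronic ED, which gives no support for assuming that a large share of men are early in recovery.

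It also stands that the share affected, the SD and n are all assumed, and that with a 10% share the numerical effect is small. This limits what can be said about size. It does not change what the mean change can be taken to show.

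**Conclusion.** The point holds as one of interpretation and labelling. Pooled, uncontrolled 1-year change in AUA-SI, the UCLA-PCI urinary and bowel domains, pads and pad weight cannot be read as a prosthesis effect, because it also contains the effect of concomitant sphincters and slings and any change after prostate cancer treatment. The first of these is the more directly documented, and the field needed to separate it is already required.

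The size is unknown. It depends on the share of men with a concomitant device or still recovering, which the documents do not give. Under the assumptions above (n = 200, SD 25, a 10-point change in those affected), the chance of a significant result with no prosthesis effect runs from about 9% at a 10% share to 79% at a 50% share. The claim does not extend to a finding that the plan attributes this change to the device, that the paired test has an inflated error rate, or that the bias must favour the prosthesis.

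**What to change.** In 8.3.5, 8.3.6 (urinary and bowel domains) and 8.3.7 (pads and pad weight):

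1. Report the before-after change as descriptive change in status over the year, without a p-value and not as prosthesis effectiveness.
2. Present it separately for men with and without a concomitant sphincter or sling, using the concurrent-procedures field.
3. As a supportive table only, show change by duration of ED in men whose etiology is prostatectomy, pelvic radiation or other pelvic surgery. State that duration of ED is an imperfect and optional proxy for time since treatment: ED may precede the treatment, and some men will have no value recorded. No conclusion should rest on one stratum. The 2-year horizon in section 2.1 concerns recovery of erections, so it should not be taken as a cut-off for urinary or bowel recovery.

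IIEF-5, EHS and the UCLA-PCI sexual domains stay as planned.

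The cost is a change of wording, one or two extra tables from fields already on the forms, and smaller strata. The sphincter or sling group may be small enough to support only counts and simple summaries.

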#### Determination of Patients for Analysis:

All enrolled patients that received a BSC penile prosthesis with data available will be included.

